4 STATISTICAL ANALYSES

If not stated otherwise the following standard types of descriptive analyses will be presented:

- Descriptive statistics for continuous data
Number of subjects, mean, standard deviation, minimum, lower quartile, median, upper quartile, maximum.
- Descriptive statistics for categorical data
Percentage bases (denominators) will be identified in the table title or footnote (i.e. all subjects at risk, all non-missing cases, all cases).
- Inferential statistics
Unless otherwise stated, all statistical tests will be performed two-sided and at a type I error probability of $\alpha=0.05$.
Unless otherwise stated, all confidence intervals (CIs) will be derived two-sided and at a confidence probability of $1-\alpha=0.95$.

Statistical Analysis Plan	Version 2.0		Page 13 of 14
Sponsor	Gesynta Pharma AB	Protocol No	GS-2001

For exploratory endpoints nominal p-values for comparison between treatments using a will be presented.

- Listings

All recorded data will be listed by subject ID, treatment group and stratification group.

4.1 Conventions

4.1.1 Baseline definition

The last non-missing measurement prior to first dose will serve as baseline for calculating changes from baseline. In practical terms this means that the general approach will use visit 2 data as the defined baseline and if that is missing, the visit 1 data will be used. For some data, e.g demographics, there is only a screening visit and this will be defined as the baseline visit in this case. Unscheduled visits will not be used as baseline visits.

4.1.2 Missing data

For the analyses of the primary endpoint and the key secondary endpoints on the FAS, missing data will be replaced using the placebo multiple imputation, (pMI) method. Details are described in the primary efficacy endpoint section. All other analyses will be performed on observed data only.

4.1.3 Study day definition

Study day will be calculated relative to the date of randomization i.e.

If Assessment date < Randomisation Date then;

$$\text{Study day} = \text{Assessment Date} - \text{Randomisation Date}$$

Else if Assessment date >= Randomisation Date then;

$$\text{Study day} = \text{Assessment Date} - \text{Randomisation Date} + 1$$

4.1.4 Completion of study definition

A subject is considered to have completed the study if he/she has completed all visits of the study including the Follow-up visit.

4.1.5 End of Study definition

The end of the study is defined as the date of the last visit of the last subject in the study.

4.1.6 Window date

The Window date in Diary information is the actual date of the event

4.2 Demographic and other background data

Demographic, baseline and disease specific subject characteristics will be summarized in frequency or sampling statistics tables for the FAS and PP population. Tables will be split by treatment group and will show pooled groups as well.

The following variables will be summarized:

Statistical Analysis Plan	Version 2.0		Page 14 of 15
Sponsor	Gesynta Pharma AB	Protocol No	GS-2001

Demographics

- Age
- Sex
- Weight
- Height
- BMI (calculated)
- Country
- Centre
- Race
- Females only: childbearing potential (Yes/No)

Disease specific subject characteristics measured at screening/baseline only

- Stratification factors i.e. Background vasodilatory treatment
- Baseline Nailfold capillaroscopy (interpretation of vasculopathy of 8 fingers, density, width and presence of giant capillaries)
- Thyroid hormones (free T3/T4, tot T4, TSH)
- SSc-related antibodies

4.3 Disposition

The disposition of subjects, presenting the number of subjects, number and reasons for discontinuations will be tabulated by visit, treatment and overall, for the Screened set. A CONSORT flow diagram on subject disposition, will be created in the CSR.

The number and percentage of subjects completing study visits and either completing or discontinuing the study, showing the reason for terminations will be presented by treatment for the FAS and PP set.

By subject listings of disposition details for discontinued subjects and subjects completing the study will be provided. In addition, a by-subject listing of the randomisation scheme and codes will be provided.

Screen failure data will be listed.

4.4 Analysis Sets

The number/percentage of subjects in the various analysis sets will be presented by treatment, for the Randomized Set. Frequencies of different reasons for exclusions from the FAS and PP set will be presented for the Randomized set.

Analyses on the FAS population will be done according to the ‘as randomized’ principle, i.e., according to the treatment group subjects were randomised to even if they may have got incorrect treatment.

Analyses on the SAS and PK set will be done according to the ‘as treated’ principle.

A listing displaying the analysis set information (including reasons for exclusion from each analysis population) on a per subject level will be created, based on the outcome of the BDRM.

Statistical Analysis Plan	Version 2.0		Page 15 of 16
Sponsor	Gesyntha Pharma AB	Protocol No	GS-2001

4.5 IMP exposure, compliance

The IMP extent of exposure (in days) will be derived as follows:

$$\text{Duration of exposure (days)} = \text{Date of last dose} - \text{Date of first dose} + 1$$

Exposure duration is based on first and last IMP date, where the first IMP date was captured on Visit 2 Day 1 exposure eCRF page and last IMP intake was taken from discontinuation page (for early discontinuations) or Visit 4 exposure eCRF page.

Number of IMP intake days is defined as the number of days IMP was taken as recorded in the diary and eCRF. When diary information indicated two replies on IMP intake on a same window date (see definition of window date in section 4.1.6) the last information was used to determine IMP intake on that day.

IMP Compliance will be calculated as the ratio of the number of IMP intake days and the IMP extent of exposure (number of days IMP should have been taken).

Compliance with IMP is defined as IMP compliance $\geq 80\%$

Non-compliance with IMP is defined as IMP compliance $< 80\%$.

A summary of the IMP extent of exposure and cumulative exposure over time, Number of IMP intake days, IMP compliance, compliance/non-compliance will be presented per treatment group for the FAS.

A by subject listing of IMP intake, IMP extent of exposure, Number of IMP intake days, cumulative exposure and IMP compliance will be provided.

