### **5.2 Administration**

The initial dose of IMP will be taken at the study site at Visit 2 under supervision of the Investigator or their staff. Subsequent doses of IMP will be self-administered by the subject, taken orally, once daily, with the exception of the final dose of IMP, which will be taken at the study site (Visit 4). The IMP will be administered with water, in the morning with food.

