2.3 Individual protocol deviations

In the course of the study, all protocol deviations will be collected, and during a Blind Data Review Meeting (BDRM) with the sponsor, protocol deviations and the consequences regarding the analysis populations and statistical analysis will be assessed.

The following protocol deviations may affect the evaluation of subject data and will be considered for exclusion from the Per-Protocol analysis:

- Violation of inclusion/exclusion criteria
- Not receiving the medication to which the subject was randomized
- Use of prohibited concomitant medication
- Non-compliance with protocol procedures
- Less than 80% compliance with IMP intake

Statistical Analysis Plan	Version 2.0		Page 12 of 13
Sponsor	Gesynta Pharma AB	Protocol No	GS-2001

Any subjects or data values excluded from analysis will be identified, along with their reason for exclusion. A complete listing of documented and derived protocol deviations and the judgment for assessment of subject disposition (i.e. analysis population membership) will be signed before database lock.

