3.4 Per-protocol Set

The Per-Protocol Set (PPS) includes all subjects of the FAS who had no major protocol deviations in a way that might affect the evaluation of the effect of the study drug(s) on the primary endpoint as determined during the BDRM.

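### SAP 4.1.2 and 5.1.3 give contradictory missing-data rules for the per-protocol primary analysis, and the SAP 4.5 compliance ratio ignores untreated days after a recorded early stop

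*SAP*

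**What the plan says.** **Compliance.** SAP 4.5 derives extent of exposure as last dose date minus first dose date plus one. On the source of the last date it says: "last IMP intake was taken from discontinuation page (for early discontinuations) or Visit 4 exposure eCRF page". Compliance is then "the ratio of the number of IMP intake days and the IMP extent of exposure (number of days IMP should have been taken"), with 80% separating compliant from non-compliant subjects, and it is summarised by arm on the FAS. Treatment is planned once daily for 28 days (−2/+1) (protocol 1.2). After the first dose, subjects dose themselves, "with the exception of the final dose of IMP, which will be taken at the study site (Visit 4") (protocol 5.2).

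**Use for the PPS.** SAP 2.3 includes "Less than 80% compliance with IMP intake" among the deviations that "will be considered for exclusion from the Per-Protocol analysis". It is the only numerical adherence item in that list, and no item names early discontinuation. SAP 3.4 excludes subjects with major deviations that could bear "on the primary endpoint as determined during the BDRM".

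**Missing data.** SAP 4.1.2 assigns pMI to the primary and key secondary analyses on the FAS, refers to the primary-endpoint section for details, and places everything else on observed data. That section, SAP 5.1.3, closes by applying the pMI process to the FAS and the PPS alike. SAP 5.1.5 and protocol 8.5.1 both plan a PPS analysis of the primary endpoint. SAP 5.1.6 adds an observed-cases run without naming its analysis set.

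**The concern.** On missing data, one planned analysis carries two written instructions. A PPS member without a week 4 diary is imputed from the placebo arm under SAP 5.1.3 and dropped under SAP 4.1.2. If this is left open until after unblinding, the choice can be made with the results in view, which weakens the PPS as a robustness check.

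On compliance, the label on the denominator promises the dosing days that were due, but for a recorded early stop the formula delivers only the days up to the last dose taken. A subject who abandons treatment after one dose is therefore tabulated as fully compliant in the FAS summary, and the untreated remainder of the four weeks can never trigger the 80% item.

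**Working it through.** **1. Missing-data rule, set side by side**

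| Analysis of the primary endpoint | SAP 4.1.2 | SAP 5.1.3 | Protocol 8.5.1 |
|---|---|---|---|
| FAS | pMI | pMI | pMI |
| PPS | observed data (falls under all other analyses) | pMI | endpoint analysed on FAS and PPS; pMI named as its primary statistical analysis |

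Only the PPS row conflicts. The specific SAP section and protocol 8.5.1 point the same way.

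**2. Size of the conflict (illustration only)**

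Inputs from SAP 1.5 and protocol 8.10: reductions of 12.0 and 4.0 attacks per week, SD 10.0, two-sided α 0.05, power 80%, dropout 10%. The plan's own figure reproduces. The normal approximation 2 × (1.96 + 0.84)² × 10²/8² gives 24.5, hence 25 per group. The exact t-test gives 25.52, hence the stated 26, with power 80.7%.

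Now assume that a fraction d in each arm lacks week 4 data, unrelated to outcome, that all of these subjects stay in the PPS, and that covariates are ignored. Under pMI the active mean becomes (1 − d) × 12.0 + d × 4.0 and the placebo mean stays at 4.0, so the expected difference is 8.0 × (1 − d):

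- d = 5%: 7.6
- d = 10%: 7.2
- d = 20%: 6.4

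On observed data it stays at 8.0. This compares the two missing-data rules; it does not measure the compliance gap.

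**3. Compliance ratio**

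SAP 4.5 ratio = intake days / (last dose date − first dose date + 1). Comparator = intake days / 28 planned days.

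| Course | SAP 4.5 | Of 28 planned days | Below 80% under SAP 4.5? |
|---|---|---|---|
| 1 dose, recorded stop | 1/1 = 100% | 1/28 = 4% | no |
| Every dose, recorded stop on day 14 | 14/14 = 100% | 14/28 = 50% | no |
| Every dose, recorded stop on day 21 | 21/21 = 100% | 21/28 = 75% | no |
| 12 intake days, recorded stop on day 14 | 12/14 = 86% | 12/28 = 43% | no |
| 10 intake days, recorded stop on day 14 | 10/14 = 71% | 10/28 = 36% | yes |
| Days 1–14, no recorded stop, on-site dose on day 28 | 15/28 = 54% | 15/28 = 54% | yes |

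The last two rows bound the gap: doses missed before a stop still count, and someone who lapses but takes the on-site Visit 4 dose is caught.

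**4. Where a planned-day threshold would fall**

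0.8 × 28 = 22.4, so 23 intake days are needed (22/28 = 79%, 23/28 = 82%). If Visit 4 falls on day 26, 27 or 29, the minimum is 21, 22 or 24. A subject who takes every dose and stops on day 23 would still pass, so a planned-day ratio alone does not identify every discontinuer.

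**The case against.** **The label can be defended.** Protocol 4.5 (QTcF rule) and protocol 7.1.6 (visits missed because of COVID-19) direct that dosing stop in stated circumstances. For those subjects no further doses were due, so a denominator ending at the last dose fits its label and a 28-day one would not. Compliance while on treatment, with discontinuation reported separately, is also an accepted convention. This stands for directed stops. It does not help the subject who simply gives up, for whom dosing to Visit 4 was still planned.

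**The 80% item is not a gate.** It is only considered at a blinded review, alongside a general item on not following protocol procedures, and protocol 8.1.3 also requires sufficient compliance with the protocol. This stands. A reader might infer that early discontinuers will be kept in the PPS, pointing to SAP 4.3, where counts of subjects "either completing or discontinuing the study, showing the reason for terminations will be presented by treatment for the FAS and PP set", and to pMI being run on the PPS. Neither supports that. A disposition table by analysis set does not decide who is in the set, and SAP 5.1.3 covers lost diaries as well as discontinuations, so imputing on the PPS makes sense even with no discontinuers in it.

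**The missing-data conflict resolves itself.** SAP 4.1.2 defers to the section that gives the opposite rule, and protocol 8.5.1 sides with that section. This largely stands and settles the direction of the correction. Protocol 8.10.1 describes a model-based imputation and leaves placebo imputation as a possible sensitivity method, but it draws no line between FAS and PPS, so it does not rescue SAP 4.1.2. The contradictory sentence remains in the plan.

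**Naming early discontinuation in SAP 2.3 would be enough.** It would bring every recorded stopper to the review. The planned-day ratio adds a graded figure that separates a stop on day 1 from one on day 25; it is the lesser half of the remedy.

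**Conclusion.** Both parts hold as defects of wording and derivation. The PPS primary analysis has two incompatible missing-data rules, of which SAP 5.1.3 is the better supported. The SAP 4.5 ratio cannot register untreated days after a recorded early stop, so the 80% item and the FAS compliance summary overstate adherence to the planned course for such subjects: 100% against 4% in the extreme case, 86% against 43% in an intermediate one. These ratios are plain arithmetic and assume only a 28-day planned course.

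The reach is limited. The primary FAS analysis uses neither the compliance ratio nor the disputed rule, since both sections apply pMI to it. Discontinuations are tabulated under SAP 4.3, and SAP 4.4 provides that "Frequencies of different reasons for exclusions from the FAS and PP set will be presented for the Randomized set". The 7.2 versus 8.0 contrast at 10% dropout is an upper-end illustration that assumes every dropout lacks week 4 data and stays in the PPS. It is not a forecast, and the plan sets no power target for the PPS. A reader might conclude that the trial's main result is at risk, or that the 80% item can never flag a discontinuer; the documents support neither. Severity: minor.

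**What to change.** Before unblinding, and preferably before the blinded data review:

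1. Amend SAP 4.1.2 to match SAP 5.1.3, with pMI on the FAS and the PPS for the primary endpoint. State in SAP 5.1.6 that the observed-cases run is done on both sets.
2. Relabel the SAP 4.5 ratio *compliance while on treatment* and keep it as a descriptive figure. For the PPS item, divide intake days by planned dosing days, from first dose to actual or scheduled Visit 4.
3. List early discontinuation as its own item in SAP 2.3 and say how it is handled for the PPS. Record protocol-directed stops separately from non-compliance; otherwise a directed stop at Visit 2 would be scored 1/28 = 4%.

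The cost is one derivation and a few sentences in SAP 2.3, 4.1.2, 4.5 and 5.1.6, with no new data. The downside is a slightly smaller PPS, with post-randomisation exclusions that may differ by arm. SAP 4.4 already plans the counts of exclusion reasons, which should be shown by arm.

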4.6 Medical history, physical examination

Medical history will be coded with the latest available version but not older than 23.1 Medical Dictionary for Regulatory Activities (MedDRA) and summarized by System Organ Class, Preferred Term, treatment group with counts and percentages for the FAS. A subject will only be counted once in a System Organ Class and a System Organ Class/Preferred Term combination.

All medical history and physical examination (full and abbreviated (digital ulcer statement)) data will be listed.

4.7 Prior and concomitant medication

Any medication taken at time of screening and all new medications taken by the subject during the study period are defined as ‘Concomitant’. Any changes of medications during the study period will also be recorded.

Prior and concomitant medications will be coded using the WHO Drug Global thesaurus in the version current at the time of study start. Coding will be performed by the CRO and agreed upon with the sponsor before data base lock. (cf. DMP). Prior and concomitant medication tables will show the frequencies of subjects by WHO Drug Global preferred term.

Statistical Analysis Plan	Version 2.0		Page 16 of 17
Sponsor	Gesyntha Pharma AB	Protocol No	GS-2001

All details of concomitant medications will also be listed including the route, dose, frequency, start and stop date and indication.

Prior and concomitant medications will be analysed based on two periods:

- 1) Prior medications: medications that the subject started to take prior to Visit 1
- 2) Concomitant medications: medications that the subject take anytime on or after Visit 1 up to Visit 5

Where dates are missing or partially missing medications will be assumed to be concomitant unless there is clear evidence (through comparison of partial dates) to suggest that the medication started and stopped prior to Visit 1 or started after Visit 5.

The following summaries will be provided:

- A summary of the number and percentage of subjects who used any prior medication by ATC (level 3) and PT, by treatment group and overall
- A summary of prohibited concomitant medications during study period, ATC (level 3) and PT, by treatment group and overall
- A summary of all allowed concomitant medications during study period, ATC (level 3) and PT, by treatment group and overall

The identification of prohibited concomitant medications will be conducted as part of the medical review.

Multiple records for a subject in the same ATC level 3 category and PT will be counted only once in each summary.

5 EFFICACY

5.1 Primary endpoint: Mean change from baseline to week 4 in number of Raynaud's Phenomenon (RP) attacks

5.1.1 Diary: Number of RP attacks

RP attacks in the daily diary

RP attacks are captured in the diary. For each RP attack the date, start time, stop time and the experienced pain (scale of 0 (No pain) to 10 (worst imaginable pain)) is captured. If an RP attack continues into the next day, the RP attack is counted on the date the attack started.

In addition to the daily entry of RP attacks in the diary, the diary is organized in such a way that patients are asked, through the previous attack details form, whether they had any RP attacks on the previous day:

- Did you have any attacks yesterday (CEPERF=Yes/No)
- Did you record them all in the diary (CECONF=Yes/No)

The replies to these questions are used for the interpretation of the RP attacks recorded in the diary in the following way:

Statistical Analysis Plan	Version 2.0		Page 17 of 18
Sponsor	Gesynta Pharma AB	Protocol No	GS-2001

If the patient answers (CEPERF=No) or the patient answers (CEPERF=Yes and CECONF=Yes), it is assumed that RP attacks on the previous day are recorded as instructed.

If the patient confirms both questions (CEPERF=Yes and CECONF=Yes), it is assumed that RP attacks on the previous day are recorded as instructed.

If the patient answers CEPERF=Yes and CECONF=No, and any RP attacks are recorded on the previous day, it is assumed that RP attacks on the previous day are recorded as instructed.

If the patient answers CEPERF=Yes and CECONF=No, and no RP attacks are recorded on the previous day, it is assumed the RP attacks on the previous day are confirmed missing.

Missing value imputation to come to number of RP attacks in the 7 days preceding a visit

For each day, starting during the baseline diary week, the number of recorded RP attacks as defined above and the number of days with confirmed RP attack information, are counted.

For the baseline week and for week 4 the number of daily attacks in the 7 most recent days before a visit (Day 1 and Day 28 (-2/+1)), will be derived by calculating the mean number of daily RP attacks on the days with RP attack information in the 7 most recent days and subsequently imputing this mean on the days with confirmed missing RP attack information in the 7 most recent days in the following way:

- 1) Summing the number of confirmed RP attacks in the 7 most recent days before a visit (total number of confirmed RP attacks)
- 2) Dividing this sum by the number of days with confirmed RP attack information in the 7 most recent days before a visit (=mean daily number of confirmed RP attacks)
- 3) Multiplying this mean number of daily attacks with 7.

This derivation results in the number of RP attacks in a week.

5.1.2 Derivation of the mean change from baseline to week 4 number of RP attacks

The primary endpoint for this study is the mean change from baseline to week 4 in the number of Raynaud's Phenomenon attacks per week as derived in 5.1.1 i.e., number of RP attacks in week 4 minus the number of RP attacks during the baseline week, where a decrease change in the number of RP attacks at week 4 compared to baseline indicates an improvement compared to baseline

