## 4 STUDY POPULATION

### 4.1 Inclusion Criteria

Individuals who meet all of the following criteria are eligible to participate in the study.

1. Subjects must provide signed and dated written informed consent before the conduct of any study-specific procedures.
2. Male and female subjects aged 18-75 years inclusive.
3. Systemic Sclerosis diagnosed according to European League Against Rheumatism (EULAR)/American College of Rheumatology (ACR) criteria ([van den Hoogen F et al. 2013](#)).  
*Subjects with signs of other autoimmune diseases (e.g. Sjögren's syndrome, myositis, rheumatoid arthritis) could be included if SSc is the dominating phenotype.*
4. Raynaud attacks typically  $\geq 7$  times per week during the last 4 weeks prior to screening despite background medication (only allowed vasodilatory therapy is calcium channel blockers or PDE-5 inhibitors).
5. Women of childbearing potential (WOCBP) must be using a highly effective method of contraception to avoid pregnancy throughout the study and for 4 weeks after the last dose of IMP in such manner that the risk of pregnancy is minimised (see [APPENDIX 12](#)).
6. Women must not be pregnant or breastfeeding.
7. Male subjects to agree to use condom in combination with use of contraceptive methods with a failure rate of  $< 1\%$  to prevent pregnancy and drug exposure of a partner, and refrain from donating sperm from the first date of dosing until 3 months after last dosing of the IMP.
8. Ability of subjects to participate fully in all aspects of this clinical trial.

In addition to fulfilling all eligibility criteria, subjects must fulfil the following criteria to be randomised:

- $\geq 7$  RP attacks during the last week of the run-in period as captured in the eDiary, with no more than 2 days without RP attacks.
- Compliance with the eDiary during the 7 most recent days prior to baseline (Visit 2), excluding the visit day itself, defined as having submitted  $\geq 5$  days of eDiary records (out of a possible 7 days) for RCS and RP during that period.

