#### ***8.5.1 Primary Efficacy Endpoint Analysis***

The analysis of the primary endpoint is conducted on the FAS (the primary analysis population) and the PPS.

For the derivation of the endpoint, the 7 most recent days prior to the date of each visit will be used. Missing data will be replaced using the mean value of the observed days. The primary analysis of the primary endpoint is mean change from baseline to week 4 in the number of RP attacks per week, and will be performed using the analysis of covariance, ANCOVA test, including the stratification factor and treatment as fixed factors and baseline levels as a covariate in the model.

The null hypothesis is that there is no difference between treatments.

The primary objective will be met if there is a p-value <0.05 with a numerical superior efficacy of the IMP versus placebo with regard to the primary endpoint, i.e. the mean change in RP attacks. There will be no adjustment for multiplicity for the primary endpoint.

Data for the primary endpoint will be presented using observed data. The primary statistical analysis of the primary endpoint will be done using the placebo multiple imputation method, pMI, and as a sensitivity analysis, the last-observation-carried-forward (LOCF).

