## 8.10 Determination of Sample Size

Power calculation for the primary efficacy endpoint is based on a two-sided t-test for independent samples with a type-I error rate of 0.05. Calculations assumed a mean change from baseline to week 4 of 12.0 for the active treatment arm versus 4.0 for the placebo arm, and a common standard deviation of 10.0, with a power goal of 80%.

Power calculations reveal that 26 subjects per group are needed to meet the power goal. To allow for a dropout rate of 10%, and some margin for uncertainty in the assumption of variation in the power calculation assumed, approximately 80 subjects will be enrolled and randomised into this study.

An estimated 50 subjects will be assessed for the secondary endpoint of mean change in peripheral blood flow using thermography and cold challenge.

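### SAP 5.1.1 fills a diary day known to hold at least one attack with a mean that can fall below 1, so a week-4 record with a reported attack can score 0

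*SAP*

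**What the plan says.** SAP 5.1.1 sorts each diary day by two replies given the next day: whether there were attacks (CEPERF) and whether they were all recorded (CECONF). CEPERF=No counts as a day with information and zero attacks. Yes/Yes counts as recorded. Yes/No with any attack on file also counts as recorded. One class is left: "If the patient answers CEPERF=Yes and CECONF=No, and no RP attacks are recorded on the previous day". Only that day is called confirmed missing.

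The weekly count is then built in three steps: sum the confirmed attacks over the 7 most recent days, divide by the number of days with confirmed information, and finish by "Multiplying this mean number of daily attacks with 7". The SAP describes this as "subsequently imputing this mean on the days with confirmed missing RP attack information in the 7 most recent days". No lower limit is set on the filled value. Protocol 8.5.1 has the same rule in substance: "Missing data will be replaced using the mean value of the observed days".

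Three other places bear on the point:
- SAP 5.2.3 step 3 multiplies the weekly count into cumulative duration, a key secondary endpoint.
- Protocol 4.1 requires at least 7 attacks in the last run-in week, "with no more than 2 days without RP attacks". Nothing similar applies at week 4.
- The eDiary (Protocol Appendix 10) tells a subject who replies that attacks were not recorded to go back and enter them.

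**The concern.** A mean fill is reasonable for a day about which nothing is known. A confirmed-missing day is different, because the subject has stated that at least one attack occurred. Filling it with an average that counts attack-free days as zeros can put less than one attack, or none, on a day when the subject reported some. The derivation then contradicts the data it is meant to summarise.

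This is the primary endpoint. The contradiction arises at low counts, which means mainly at week 4 and in subjects who have improved. A week scored 0 also leaves the logarithm of cumulative duration undefined in SAP 5.2.3.

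**Working it through.** **Scale.** Protocol 8.10 assumes changes of 12.0 and 4.0, so a difference of 8.0, with SD 10.0, two-sided 0.05 and 80% power. The exact two-sample t solution is 25.52, rounded up to the stated 26 per group (power 80.7%). With about 40 per group, power is 94.2% and the standard error of the difference is 10 x √(2/40) = 2.24. This point does not change the sample size; the figures only give a scale.

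**The rule.** Let S be the attacks recorded on d days with information, k the confirmed-missing days, and m = S/d. The score is 7m. When d + k = 7 this equals S + k x m, so each confirmed-missing day receives m.

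**Where the error is certain.** The true count on a confirmed-missing day is at least 1. If m < 1, that is 7m < 7, the fill is too low whatever caused the gap. Example weeks with six days of information and one confirmed-missing day:

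| Six days with information | m | SAP score | Fill = larger of 1 and m | Fill = attack-day mean, minimum 1 |
|---|---|---|---|---|
| 0,0,0,0,0,0 | 0 | 0 | 1 | 1 |
| 0,0,0,0,0,1 | 0.17 | 1.17 | 2 | 2 |
| 2,0,0,2,0,2 | 1.00 | 7.0 | 7.0 | 8.0 |
| 1,1,1,1,1,2 | 1.17 | 8.17 | 8.17 | 8.17 |

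At baseline, at least 7 attacks over at most 7 days gives m ≥ 1, provided the attacks used for eligibility are the ones scored. The certain error, including the zero score, is therefore a week-4 matter.

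**Direction at higher rates.** The documents give neither the frequency of such days nor the distribution of daily counts. The check assumes Poisson daily counts, 40,000 simulated weeks per setting, and looks at weeks with exactly one confirmed-missing day. Mechanism (a): a whole attack day goes unentered regardless of its count. Mechanism (b): each attack is independently unentered with probability 0.2, and a partly entered day is taken as complete, as the SAP does. The table shows mean error in attacks per week.

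| True rate per week | (a) SAP | (a) attack-day mean | (b) SAP | (b) attack-day mean | Scored 0, (a) / (b) |
|---|---|---|---|---|---|
| 3.5 | -0.88 | -0.04 | -0.62 | +0.15 | 14.4% / 7.2% |
| 7 | -0.67 | +0.01 | -0.23 | +0.35 | 1.1% / 0.4% |
| 8 | -0.62 | 0.00 | -0.12 | +0.41 | 0.6% / 0.2% |
| 16 | -0.29 | +0.01 | +0.69 | +0.93 | 0 / 0 |
| 20 | -0.20 | 0.00 | +1.09 | +1.25 | 0 / 0 |
| 28 | -0.09 | -0.01 | +1.82 | +1.88 | 0 / 0 |

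**Treatment difference.** Assume a baseline of 20, so week-4 means of 20 - 12 = 8 (GS-248) and 20 - 4 = 16 (placebo). Under (a), with 5 to 10% of attack days unentered and rates varying between subjects, arm means shift by -0.11 to -0.32 (GS-248) and -0.09 to -0.39 (placebo). The difference shifts by -0.04 to +0.07; 0.07/2.24 is about 3% of a standard error.

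Mechanism (b), with its heavier 20% loss of attacks, gives more. Using weeks with one or two confirmed-missing days out of 40,000:
- At 8 per week: (13,821 x -0.121 + 3,681 x -0.251)/40,000 = -0.06.
- At 16 per week: (11,483 x 0.693 + 2,149 x 1.378)/40,000 = +0.27.

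That is about 0.34 attack in favour of GS-248, or 4% of 8.0 and 15% of a standard error. It comes mostly from overfilling at the higher rate, which a floor of 1 does not touch.

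**The floor.** If m < 1 and the truth is at least 1, raising the fill to 1 cannot move it further from the truth, under any mechanism. In simulated affected weeks at 3.5 attacks per week, mean absolute error fell from 0.94 to 0.44 in one setting and from 0.73 to 0.14 in another.

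**The case against.** The case for leaving the rule alone has real content.

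- **It follows the protocol.** Protocol 8.5.1 specifies the mean of the observed days, so any change is a departure that must be declared. This stands, and the fix allows for it.
- **Such days should be few.** The diary prompts the subject to enter the omitted attacks, and SAP 5.2.3 does not exclude late-recalled entries. This stands, although no document says how few.
- **The zero score is rare.** At 8 attacks per week it is 0.6% or less of weeks with one confirmed-missing day, and about 0 at 16 or more. This stands under the Poisson assumption.
- **The trial-level effect is small and the rule is the same in both arms.** With no treatment effect the error falls alike on both, and no inflation of the type I error is shown. This stands.
- **An attack-day mean may be worse than the present rule.** A day is confirmed missing only if nothing was entered, which may select days with few attacks. Under (b) the attack-day mean overstates at every rate tested. This stands, and it rules that fill out as the primary method.

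None of this answers the narrower point that a fill below 1 contradicts the subject's own reply.

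**Conclusion.** Wrong as written; low severity. The only day SAP 5.1.1 defines as missing carries a report of at least one attack, and the rule can give it less than one or none. That follows from the text and needs no assumption about the data.

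A reader might infer three stronger things, which the documents do not support:
- **That the primary count is always understated.** This is certain only when the mean over days with information is below 1 per day. Above that, the sign depends on which days go unentered: at 16 per week it is -0.29 under (a) and +0.69 under (b). The documents do not say which applies.
- **That the benefit of GS-248 is materially overstated.** The calculated effect on the difference is about 0.1 attack or less under (a), with no settled sign, and about 0.3 under the harsher version of (b), against a planned 8. Both rest on assumed rates of unentered attacks and an assumed baseline of 20.
- **That filling with the attack-day mean removes the bias.** It does so under (a) only.

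**What to change.** Before unblinding, amend SAP 5.1.1 so that each confirmed-missing day is filled with the larger of 1 and the mean over the days with information, at both baseline and week 4. The weekly count is then recorded attacks plus these fills. An equivalent form is 7m + k x max(0, 1 - m), which leaves any day without a reply treated as the present formula treats it.

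Carry the revised count into step 3 of SAP 5.2.3, and state that duration is missing if no confirmed attack in the week has a duration. The floor cannot supply one: in the six-zero example, step 2 would still divide by zero confirmed attacks. List the departure from Protocol 8.5.1 in SAP 2.2. Use the mean over attack days, with a minimum of 1, only as a sensitivity analysis. The blinded diary review that the SAP already reports could also count confirmed-missing days, which would show whether the point matters in practice.

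Cost: about one line of derivation code, a short SAP edit and an entry in SAP 2.2, with no new data. The one-step formula becomes a two-part sum, and a few week-4 counts become slightly less favourable. Every week the floor changes moves no further from its true count, but an arm mean in which underfilled and overfilled weeks happened to cancel could move slightly upward.
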